7.2. HIV Viral Load Assessment and CD4+ Cell Counts

HIV viral load and CD4+ cell counts will be evaluated for HIV-infected subjects. For analysis, the HIV viral load assessment at each time point will be categorized as follows:

- **<20 copies/mL:** Both undetectable (ie, values below the limit of detection ["NOT DETECTED"]) and non-quantifiable (ie, <20 copies/mL) HIV viral load.
- **20-200 copies/mL:** HIV viral loads ranging from 20 to 200 copies/mL.
- **>200 copies/mL:** More than 200 copies/mL of HIV viral load.

A summary table will be generated based on the above categorization of the HIV viral loads. The table will show the number and percentage of subjects under each category at baseline and post-baseline time points and by vaccination schedule. A cross tabulation will also be generated for those categories. The cross tabulation will show the number and percentage of subjects in each category at baseline against other time points.

Subject-specific profiles will be generated for the HIV viral load and CD4+ cell counts. The graphs will be generated separately for those subjects whose baseline HIV viral load falls within a category (ie, <20 copies/mL, 20-200 copies/mL and >200 copies/mL).

In addition, a listing (also showing all the HIV viral loads and CD4+ cell count assessments) will be generated.

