11.8 Protocol Safety Review Team and Protocol Safety Review Team Reviews

16.2.3 DoD Research Monitor

SYNOPSIS

A Randomized, Observer-blind, Placebo-controlled, Two-part, Phase 2 Study to Evaluate the Safety, Tolerability and Immunogenicity of Two Prime-boost Regimens of the Candidate Prophylactic Vaccines for Ebola Ad26.ZEBOV and MVA-BN-Filo.

The sponsor, in collaboration with Bavarian Nordic (BN) and Walter Reed Army Institute of Research (WRAIR), is investigating the potential of a prophylactic Ebola vaccine regimen comprised of the following 2 candidate Ebola vaccines:

Ad26.ZEBOV is a monovalent vaccine expressing the full length Ebola virus (EBOV, formerly known as *Zaire ebolavirus*) Mayinga glycoprotein (GP), and is produced in the human cell line PER.C6[®].

MVA-mBN226B, further referred to as Modified Vaccinia Ankara (MVA)-BN-Filo[®], is a multivalent vaccine expressing the Sudan virus (SUDV) GP, the EBOV GP, the Marburg virus (MARV) Musoke GP, and the Tai Forest virus (TAFV, formerly known as Côte d'Ivoire ebolavirus) nucleoprotein (NP), and is produced in chicken embryo fibroblast cells. The EBOV GP expressed by MVA-BN-Filo has 100% homology to the one expressed by Ad26.ZEBOV.

Two populations will be studied in this protocol: healthy adults and human immunodeficiency virus (HIV)-infected adults, ages 18-70 years inclusive, will be enrolled.

Ad26.ZEBOV and MVA-BN-Filo will be evaluated as a heterologous prime-boost regimen. The first schedule to be evaluated is prime vaccination with MVA-BN-Filo followed by a boost with Ad26.ZEBOV 14 days later. In the second schedule, Ad26.ZEBOV is used to prime a filovirus-specific immune response and MVA-BN-Filo is used to boost the immune response 28 days later. The EBOV GP that circulated in West Africa has 97% homology to the EBOV GP used in this vaccine regimen.

STUDY RATIONALE

- Enlarge the safety and immunogenicity database for the Ad26.ZEBOV/MVA-BN-Filo 1, 29-day prime-boost regimen in healthy adults.
- Assess the safety and immunogenicity of Ad26.ZEBOV/MVA-BN-Filo 1, 29-day prime-boost regimen in HIV-infected subjects and determine the effect of vaccination on HIV disease.
- Enlarge the safety and immunogenicity database for MVA-BN-Filo/Ad26.ZEBOV 1, 15-day prime-boost regimen in healthy adults and HIV-infected adults.

OBJECTIVES AND HYPOTHESIS

Primary Objectives

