9.2.3. Exploratory Endpoints

Additional exploratory analyses may be performed to further investigate study vaccine-elicited immune responses. The exploratory endpoints might include but are not limited to the following:

- Magnitude, kinetics and durability of humoral immune responses to EBOV GP, including neutralizing antibody response measured in titers that inhibit viral infection by a certain percentage (IC_{50, 80 or 90}).
- Magnitude, kinetics and durability of cellular immune responses for EBOV GP (EBOV GP specific T cell responses will be measured as the number of IFN- γ producing cells by ELISpot analysis).
- Comparison between healthy and HIV-infected adults of the kinetics and durability of humoral and cellular immune responses to EBOV GP of Ad26.ZEBOV/MVA-BN-Filo and MVA-BN-Filo/Ad26.ZEBOV regimens.
- Kinetics and durability of humoral immune responses, including the development of neutralizing antibodies, in healthy and HIV-infected adults for other filovirus GP (binding antibody response measured in ELISA units/mL and/or endpoint-titers; neutralizing antibody response measured as titers that inhibit viral infection by a certain percentage [IC_{50, 80 or 90}]).
- Kinetics and durability of cellular immune responses in healthy and HIV-infected adults for other filovirus GP (EBOV GP specific T cell responses will be measured as the number of IFN- γ producing cells by ELISpot analysis or the percentage of CD4+ or CD8+ T cells producing IFN- γ , tumor necrosis factor- α (TNF- α) and/or interleukin (IL)-2 by intracellular cytokine staining [ICS]).
- Comparison of kinetics and durability of humoral and cellular immune responses to the other filovirus GP, of Ad26.ZEBOV/MVA-BN-Filo and MVA-BN-Filo/Ad26.ZEBOV regimens between healthy and HIV-infected adults.
- Comparison of kinetics and durability of humoral and cellular immune responses to the EBOV other filovirus GP of Ad26.ZEBOV/MVA-BN-Filo and MVA-BN-Filo/Ad26.ZEBOV regimens between adults aged 18-50 and aged 51-70.
- Frequency, magnitude, and durability of anti-vector responses in healthy and HIV-infected adults (measured by ELISA, virus neutralization assay [VNA] and/or plaque reduction neutralization test [PRNT]).
- Time course of CD4+ count in HIV-infected adults.

- Changes in HIV RNA and HIV specific immune response (using HIV antigens in place of Ebola GP) associated with vaccination with Ad26.ZEBOV/MVA-BN-Filo and MVA-BN-Filo/Ad26.ZEBOV regimens in HIV-infected adults.

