- CD4+ cell count for HIV-infected subjects at screening, on Day 1, on the day of the boost vaccination, at 21 and 42 days after the boost vaccination and at 6 months and 1 year after the boost vaccination.
- Serology: HIV type 1 or HIV type 1/2 at screening.

Laboratory abnormalities will be determined according to the Toxicity Table for Use in Trials Enrolling Healthy Adults ([Attachment 2](#)).

Electrocardiogram

A single, 12-lead ECG will be performed at screening for subjects >50 years and interpreted locally. Additional ECG monitoring may be done at other time points during the study if clinically indicated based on signs and symptoms.

During the collection of ECGs, subjects should be in a quiet setting without distractions (eg, television, cell phones). Subjects should rest for at least 5 minutes before ECG collection and should refrain from talking or moving arms or legs.

Vital Signs (blood pressure, pulse/heart rate, body temperature)

Vital sign measurements will be performed at the time points indicated in the [Time and Events Schedule](#). Blood pressure and pulse/heart rate measurements will be assessed (at rest) with a completely automated device. Manual techniques will be used only if an automated device is not available. Confirmatory measurements can be performed if inconsistent with a prior measurement.

Either oral or axillary body temperatures may be measured and the site of measurement must be captured in the CRF.

Physical Examination

A full physical examination including height and body weight will be performed at screening. Calculation of the body mass index (BMI), will be recorded in the CRF. At other visits, an abbreviated, symptom-directed physical examination will be performed as indicated based on any clinically relevant issues, clinically relevant symptoms and medical history. The symptom-directed physical examination may be repeated if deemed necessary by the investigator. Physical examinations will be performed by the investigator or by a designated medically-trained clinician.

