2. GENERAL ANALYSIS DEFINITIONS

The type I error rate (α) is set to 0.05 and corresponding 2-sided 95% confidence intervals (CIs) will be calculated wherever applicable. Adjustment of the α (type I error) level due to multiplicity is not applicable for this study as no planned formal statistical hypothesis testing will be performed.

Analysis and evaluation are defined separately for each parameter later in this document together with the description of rules for handling missing or incomplete data. The analyses will include vaccinated subjects with respect to the actual vaccine administered. For instance, if a subject is randomized to the Ad26.ZEBOV followed by MVA-BN-Filo vaccination schedule but is inadvertently vaccinated according to the MVA-BN-Filo followed by Ad26.ZEBOV vaccination schedule, the subject will be included in the latter vaccination schedule. Also, subjects who receive only the first (dose 1) vaccination will be included in the vaccination schedule with the corresponding dose 1 vaccine. On the other hand, subjects who will receive a homologous regimen (ie, Ad26.ZEBOV followed by another Ad26.ZEBOV or MVA-BN-Filo followed by another MVA-BN-Filo) will be excluded from summary analyses (ie, tables and graphs) and listed separately.

In general, the study data will be analyzed as follows:

- Categorical variables will be summarized with a frequency table presenting counts and percentages.

- Continuous variables will be summarized using the following statistics, as appropriate: number of observations, arithmetic mean, geometric mean, corresponding 95% confidence interval (CI), standard deviation, standard error, median, quartiles (Q1 and Q3), minimum and maximum.

Baseline value will be defined as the value of the last available assessment performed prior to dose 1 administration, unless specified otherwise.

For safety assessments, the *baseline value* will be an assessment performed prior to or on the date (only if time of assessment is missing) of the dose 1 administration. The baseline value for immunogenicity assessments will be an assessment performed before or on the date of dose 1 administration. In case of multiple values, the value closest to the vaccination will be used as the baseline.

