7.3. Clinical Laboratory Tests

This section concerns the clinical laboratory test data (except HIV viral loads and CD4+ cell counts in HIV-infected subjects). The analysis of the laboratory assessments will be based on the Food and Drug Administration (FDA)'s Toxicity Grading Scale for Healthy Adult and Adolescent Volunteers Enrolled in Preventive Vaccine Clinical Trials (Attachments 3 and 4). In case no toxicity grades are defined for a test, the abnormalities above or below the normal range will be used.

It is important to note that clinically relevant changes occurring during the study are recorded in the AE section of the eCRF up to 42 days post dose 2 visit.

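### SAP 7.2 specifies no group-level or active-versus-placebo summary of CD4+ count or change from baseline, only subject profiles and a listing

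*SAP*

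**What the plan says.** The Protocol Synopsis (Study Rationale) says the study is to "determine the effect of vaccination on HIV disease". That phrase sits in the bullet on the 29-day Ad26.ZEBOV then MVA-BN-Filo regimen in HIV-infected subjects. Protocol 9.2.3 lists, among endpoints that might be examined, "Time course of CD4+ count in HIV-infected adults". Protocol 9.3.1 schedules "CD4+ cell count for HIV-infected subjects at screening, on Day 1, on the day of the boost vaccination, at 21 and 42 days after" (meaning post-boost). Further samples follow at 6 months and 1 year, seven time points in all.

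SAP 7.2 treats the two HIV markers differently. For the viral-load categories, "The table will show the number and percentage of subjects under each category at baseline and post-baseline time points and by vaccination schedule", and a cross tabulation against baseline follows. For CD4+ the section offers "Subject-specific profiles will be generated for the HIV viral load and CD4+ cell counts", drawn separately by baseline viral-load category with no split by arm stated, and "a listing (also showing all the HIV viral loads and CD4+ cell count assessments) will be generated".

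SAP 7.3 covers the other laboratory tests, "except HIV viral loads and CD4+ cell counts in HIV-infected subjects". SAP 3, which lists changes to the planned analysis, mentions no change to the CD4+ endpoint.

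**The concern.** Individual lines and a listing show no average change and make no use of the control group. Protocol 3.2 gives the placebo arm that very purpose: to show how often and how much clinical and immunologic measures change without the vaccines, up to 6 months post-boost.

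The control matters more than usual for CD4+. Protocol 4.1.2 lets untreated subjects with CD4+ of at least 350 cells/µL into Part 2, and Protocol 8 allows untreated subjects to start antiretroviral therapy during the study. A subject's CD4+ line can therefore move because of treatment start, natural variation or vaccination. A randomised contrast balances the first two on average; a set of individual plots does not.

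At stake is whether the study report can give a number, with its uncertainty, for CD4+ change in vaccinated relative to placebo subjects. Followed as written, SAP 7.2 leaves it to describe plots of up to 275 people.

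**Working it through.** **Step 1. Does any other part of the SAP commit to a CD4+ table?**

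- SAP 2: "Continuous variables will be summarized using the following statistics, as appropriate". This is conditional, and the same section says that analyses are defined parameter by parameter later. For CD4+ the later section is 7.2.
- SAP 2.1: the window rules mention tables of descriptive statistics per time point. CD4+ is excepted from the per-period presentation and has its own rule for choosing a value when only unscheduled visits exist. This supports a per-visit display but names none.
- SAP 2.4: safety data are presented for active versus placebo within part, cohort and interval. CD4+ is not named.
- SAP 7.3: CD4+ is excluded.

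These passages are compatible with a CD4+ table, but none requires one. No passage names a CD4+ mean, change from baseline, interval or contrast.

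**Step 2. Planned numbers.** The documents state no SD, effect size or precision for CD4+; Protocol Table 5 concerns ELISA levels only. Applying 4:1 to the HIV-infected cohorts gives 25 → 20 and 5 (Part 1), 200 → 160 and 40 (Part 2 Group 1), 50 → 40 and 10 (Part 2 Group 2). The sum is 275, and the splits match Protocol Table 1. The pooled 14-day schedule is 20 + 40 = 60 active and 5 + 10 = 15 placebo.

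**Step 3. Precision of the contrast that is not planned.** For the difference in mean change, active minus placebo, with a common SD:

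half-width = t(0.975, n1 + n2 − 2) × SD × √(1/n1 + 1/n2)

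- Part 2 Group 1: 1.972 × √(1/160 + 1/40) = 1.972 × 0.1768 = 0.349 SD
- Pooled 14-day: 1.993 × √(1/60 + 1/15) = 1.993 × 0.2887 = 0.575 SD
- Part 2 Group 2: 2.011 × √(1/40 + 1/10) = 2.011 × 0.3536 = 0.711 SD
- Part 1: 2.069 × √(1/20 + 1/5) = 2.069 × 0.5 = 1.034 SD

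In cells/µL, over an assumed range for the SD of change:

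| Comparison (active vs placebo) | SD 75 | SD 100 | SD 150 | SD 200 |
|---|---|---|---|---|
| Part 2 Group 1 (160 vs 40) | 26 | 35 | 52 | 70 |
| Pooled 14-day (60 vs 15) | 43 | 58 | 86 | 115 |
| Part 2 Group 2 (40 vs 10) | 53 | 71 | 107 | 142 |
| Part 1 (20 vs 5) | 78 | 103 | 155 | 207 |

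**Step 4. Which visits have a placebo comparison?** Each part is unblinded only after its last subject's 6-month post-boost visit and database lock (Protocol 5). Boost day, 21 and 42 days and 6 months are therefore scheduled for both arms. At 1 year, only placebo subjects who reach the visit before unblinding must attend, so the placebo group may be smaller and is not a random subset.

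**The case against.** The best defence is that the study is descriptive, no formal testing is planned, and the CD4+ endpoint is exploratory, in a list that the protocol says might apply. Its wording asks for a time course and names no contrast; subject profiles over time literally show that. Protocol 11.4 says only that comparative safety analyses may be considered. This stands, and it limits the weight of the point. It does not remove it: the request is for descriptive statistics with confidence intervals, which SAP 2 already prescribes wherever applicable, and needs no test.

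A second defence is that the general rules in SAP 2, 2.1 and 2.4 already cover CD4+. They might, so it would be too strong to say that the SAP rules out a by-arm summary. But they do not settle the matter, and one sentence in 7.2 would.

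A third is that HIV safety is covered elsewhere. Viral load is tabulated and was the subject of an interim analysis with an unblinded package for the IDMC (SAP 4). Clinically relevant laboratory changes are recorded as adverse events until 42 days post-boost. This is partial cover: viral load is a different marker, and adverse event reporting would not capture a modest mean shift.

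Two limits also stand. The rationale phrase about HIV disease belongs to the 29-day regimen; the 14-day bullet speaks only of enlarging the safety and immunogenicity database. And with untreated subjects enrolled, the SD of change could exceed 150 cells/µL.

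**Conclusion.** The gap is real but one of specification. SAP 7.2 commits to no group-level or placebo-controlled summary of CD4+ count or change, and the general rules do not supply one. The contrast best supported by the rationale, Part 2 Group 1, would have a half-width of about 0.35 SD (35 to 52 cells/µL at an SD of 100 to 150). The 14-day contrasts would be wide: about 0.58 SD pooled and 0.71 SD in Part 2 Group 2.

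These figures assume planned numbers with no missing data, a common SD in both arms, and an SD of change that is assumed.

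A reader might infer three stronger things that the documents do not support:

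- That the effect of vaccination on CD4+ cannot be estimated. It can: CD4+ is measured repeatedly in randomised arms and every value is listed. The estimate is simply not planned.
- That CD4+ is the study's main marker of HIV disease. The documents do not rank it so; its time course is an exploratory endpoint.
- That there are no placebo data at 1 year. Protocol 3.1 and 5 require placebo subjects who reach that visit before unblinding to attend, and 3.1 expects some Part 1 subjects to reach it before then.

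**What to change.** Add to SAP 7.2 one descriptive table for HIV-infected subjects:

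- CD4+ count and change from baseline (n, mean, SD, 95% CI) by time point, for active and placebo within each part and schedule, and for the pooled 14-day schedule.
- The active-placebo difference in mean change with a t-based 95% CI at boost day, 21 and 42 days and 6 months post-dose 2. Make Part 2 Group 1 the primary display and label the 14-day contrasts as imprecise.
- One-year values shown descriptively, with a note that only placebo subjects who reached the visit before unblinding contribute.

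Keep the profiles and the listing, and label the table exploratory, without a hypothesis test.

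The cost is one table shell and a few lines of SAP text on data already scheduled for collection. The SAP introduction says that enrolment and follow-up are complete, so no visit or sample changes. The downside is one more exploratory table with wide intervals in the smaller groups, which a reader could mistake for evidence of no effect unless the imprecision is stated.

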7.3. Clinical Laboratory Tests

This section concerns the clinical laboratory test data (except HIV viral loads and CD4+ cell counts in HIV-infected subjects). The analysis of the laboratory assessments will be based on the Food and Drug Administration (FDA)'s Toxicity Grading Scale for Healthy Adult and Adolescent Volunteers Enrolled in Preventive Vaccine Clinical Trials (Attachments 3 and 4). In case no toxicity grades are defined for a test, the abnormalities above or below the normal range will be used.

It is important to note that clinically relevant changes occurring during the study are recorded in the AE section of the eCRF up to 42 days post dose 2 visit.

7.3.1. Definitions

In determining toxicity grades, the following rules will be applied:

- Worst grades/abnormalities are determined over the entire period (eg, Post-dose 1 or Post-dose 2) separately, including all post-baseline measurements of the corresponding period.
- The abnormalities “abnormally low” and “abnormally high” are considered equally important and both abnormalities are shown in the tables. (This means that the sum of the percentages can exceed 100%).
- If a laboratory value falls within the grading as specified in the grading table but also within the local laboratory normal limits, the value is considered as normal or Grade 0.
- Laboratory results falling between the grading scales will be allocated to the adjacent worst-case grade (because the scale for some parameters in the grading table is not continuous as there may be zones where toxicity grade definitions do not exist).

An abnormality (toxicity grade or abnormality based on normal ranges) will be considered as following vaccination in a period and/or phase if it is worse than the corresponding baseline record. If the baseline value is missing, the abnormality is always considered as following vaccination. A shift from “abnormally low” at baseline to “abnormally high” post-baseline (or vice versa) is also considered as an abnormality following vaccination.

